8.6.2 Adverse Events

All AEs occurring during the study will be recorded and classified on the basis of MedDRA terminology. Descriptions of AEs will include the date of onset, the date the AE ended, the severity of the AE, the relationship to the study device, the action taken to treat the AE, and the outcome. All reported treatment—emergent AEs (TEAEs) will be summarized by the number of subjects (or eyes, as appropriate) reporting AEs, system organ class, severity, seriousness, and relationship to study device. TEAEs are those AEs with onset on or after the date of the first study device use.

Serious adverse events will be summarized at the subject and eye levels.

Adverse events will be summarized by severity. Each subject (or eye, as appropriate) will be counted only once within a system organ class or a preferred term by using the AEs with the highest severity within each category.

Adverse events will be summarized by relationship to study device. Each subject (or eye, as appropriate) will be counted only once within a system organ class or a preferred term by using the AEs with the greatest relationship within each category.

All information pertaining to AEs noted during the study will be listed by subject, detailing verbatim given by the Investigator, preferred term, system organ class, start

date, stop date, severity, action taken, and device relatedness. The AE onset will also be shown relative (in number of days) to the day of initial use of the study device.

Serious adverse events (SAEs) will be tabulated.

In addition, a list of subjects who discontinued from the study and a list of subjects who experienced SAEs will also be provided.

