7.2 Procedures for Evaluating Adverse Events

Throughout the course of this study all efforts will be made to remain alert to reportable AEs. If an AE occurs the first concern will be the safety of the subject and appropriate medical intervention will be made. All SAEs, ocular and systemic, must be recorded and reported as required.

All reportable AEs occurring after signing of informed consent and through the subject's end of participation in the study must be reported. All reportable AEs must be followed until the event resolves or stabilizes. This may imply that follow-up will continue after the subject has left the study, and that additional evaluations may be requested by the Sponsor.

Ocular AEs of possible clinical significance should be photo-documented and shared with the Medical Monitor in electronic form.

When evaluating for reportable AEs, the Investigator should refer to the definitions for AEs to determine:

- Whether the event is serious (refer to [Section 7.1.1](#) and [Section 7.1.2](#))
- Whether the event is severe (refer to [Section 7.1.6](#))
- Whether the event is significant (refer to [Section 7.1.2](#) and [Section 7.1.3](#))
- Whether the event is related to the study device (refer to [Section 7.1.5](#))

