8.1 Study Endpoints

8.1.1 Primary Safety Outcomes

The primary safety outcome is the rate of serious adverse events at the subject and eye levels.

[REDACTED]

[REDACTED]

[REDACTED]

[REDACTED]

[REDACTED]

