8.3 Sample Size

The FDA recommended a sample size of 50 completed subjects. The sample size is not based on statistical hypothesis tests. Enrollment of 70 subjects will allow for early discontinuation of up to 28% of the subjects to achieve a final sample size of 50 subjects.

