8.5 Study Populations

8.5.1 Full Analysis Set (FAS)

The FAS will consist of all dispensed subjects for subject level summaries and, for eye level summaries, both of their eyes.

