8.5.3 Safety Set

The FAS will be used to evaluate safety outcomes.

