8.6 Statistical Analysis

8.6.1 Methods of Analysis

General Methods

Continuous data will be summarized using sample size (n), mean, standard deviation (SD), median, minimum, and maximum. Categorical data will be presented using the total counts for each category and corresponding percentages. The denominator for each percentage will be the number of subjects or eyes with non-missing data unless otherwise indicated.

Data from the FAS will be used for analysis unless otherwise specified.

For each assessment, the baseline value will be defined as the last observation before the first insertion of the study lenses. Change from baseline will be computed as follow-up value minus baseline value.

As customary for contact lens trials, eyes will be treated as independent sampling units in eye level analyses unless otherwise noted.

Listings of data will be produced in addition to tables of summary statistics.

The proportion of subjects with non-missing monocular UDVA data for both eyes at the 3-Month Visit who achieved monocular UDVA of 20/40 or better in both eyes at the 3-Month Follow-up Visit will be presented.

As a sensitivity analysis, the summary will be produced using the PP Set.

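### As a measure of 3-month risk, the SAE rate is pulled down by early discontinuation; an exposure-adjusted companion figure would correct this from data already collected

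*Combined protocol and SAP*

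**What the plan says.** Section 8.1.1 defines the outcome: "The primary safety outcome is the rate of serious adverse events at the subject and eye levels". The readable text gives no denominator, time unit or estimator for that rate, and Section 8.6.2 adds only "Serious adverse events will be summarized at the subject and eye levels" and that SAEs will be tabulated.

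The denominator has to be assembled from three other places:

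- Section 8.5.3: "The FAS will be used to evaluate safety outcomes".
- Section 8.5.1: "The FAS will consist of all dispensed subjects for subject level summaries and, for eye level summaries, both of their eyes". No minimum wear is required.
- Section 8.6.1: "The denominator for each percentage will be the number of subjects or eyes with non-missing data unless otherwise indicated".

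The collection window is in Section 7.2. It begins "All reportable AEs occurring after signing of informed consent" and closes when the subject's participation ends. Events already open are followed beyond that, but new ones are not sought.

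The loss allowance is in Section 8.3: "Enrollment of 70 subjects will allow for early discontinuation of up to 28% of the subjects to achieve a final sample size of 50 subjects".

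Section 8.6.7 summarises exposure in days, and Section 8.6.2 lists each AE's onset in days from first device use. The readable plan never brings the two together.

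**The concern.** A subject who stops after a few nights counts as one full unit in the denominator, the same as a subject who wears the lenses for 90 days. An SAE that begins after that subject has exited cannot enter the numerator. The crude proportion therefore falls as more subjects leave early, with no change in the hazard of the lens.

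Early exit is built into the design. Sections 3.3.3 and 6.1.10 require discontinuation after a missed 1-Day or 1-Week Visit, and Section 6.1.5 calls for it at Month 1 if lens performance is unacceptable. This is the primary safety outcome of a 3-month single-arm study, so a reader is likely to take the figure as the risk over about 3 months of wear. The same reasoning applies to the eye-level figure.

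**Working it through.** **Inputs from the plan.** Completer target 50, loss allowance 28% and enrolment 70 (Section 8.3); follow-up to Day 90 (Section 3.6); denominator all dispensed subjects (Sections 8.5.1 and 8.5.3).

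**Assumptions, not in the plan.** All of the allowed loss falls on dispensed subjects; the SAE hazard is constant over 90 days; exit is unrelated to SAE risk; the exit day is *t*.

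**Step 1: reproduce the plan's figure.** 50 / (1 − 0.28) = 69.4, rounded up to 70, which agrees with Section 8.3. Losing 20 of 70 is 28.6%.

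**Step 2: relative understatement.** Let *d* be the share of dispensed subjects who leave at day *t*, and *R* the 3-month risk. For small *R* the expected crude proportion is about *R* × [(1 − *d*) + *d* × *t*/90]. The relative understatement is therefore *d* × (1 − *t*/90).

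| Exit day | *d* = 0.28 | *d* = 20/70 |
|---|---|---|
| 60 | 0.28 × 30/90 = 9.3% | 9.5% |
| Uniform over 90 days (mean 45) | 0.28 × 45/90 = 14.0% | 14.3% |
| 30 | 0.28 × 60/90 = 18.7% | 19.0% |
| 7 | 0.28 × 83/90 = 25.8% | 26.3% |
| 0 (upper limit) | 28.0% | 28.6% |

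Using the exact exponential form with 3-month risks of 0.5%, 1% and 5% moves these by less than 0.3 percentage points.

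**Step 3: one SAE among 70 dispensed, 20 leaving early.** The crude figure is 1/70 = 1.43%. The exposure-adjusted figure is 1 / (50 + 20 × *t*/90) per subject with 90 days of exposure:

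- Day 60: 1/63.33 = 1.58 per 100
- Day 45: 1/60 = 1.67 per 100
- Day 30: 1/56.67 = 1.76 per 100
- Day 7: 1/51.56 = 1.94 per 100

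**Step 4: how the assumptions move the result.**

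- *Losses before dispensing.* If, for illustration, 10 of the 20 losses came before dispensing, 60 would be dispensed and 10 would leave. Then *d* = 10/60 = 16.7%, and Day-30 exits give 0.167 × 60/90 = 11.1% instead of 19%.
- *Front-loaded risk.* If a fraction *f* of the 3-month risk falls before exit, the understatement is *d* × (1 − *f*). With *d* = 20/70 this is 14.3% for *f* = 0.5 and 7.1% for *f* = 0.75.
- *No SAE.* Both figures are zero and nothing is understated.

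**The case against.** The crude proportion among all treated subjects is a valid descriptive statistic. Section 8.2 tests no hypothesis, and the readable text does not call the SAE rate a 90-day risk. Exposure, reasons for discontinuation and lists of discontinued and SAE subjects are all to be reported, so a careful reader could see the context. This stands, and it is why the crude figure should be kept.

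The absolute effect is also small beside the imprecision. With 1 SAE in 70 the gap is about 0.3 to 0.5 percentage points for exits at Day 30 to Day 7, against an exact 95% interval of 0.04% to 7.7%. With no SAE, the one-sided 95% upper bound is 1 − 0.05^(1/70) = 4.2%. This also stands.

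Several design features limit the bias. A subject who leaves because of an SAE is already in the numerator. Under Section 6.1.12 a subject with an ongoing AE is not exited until it resolves or stabilises. Exit assessments are sought for early leavers. A refit restarts the visit sequence, so some subjects may be observed beyond 90 days. None of these captures an SAE that starts after an early exit.

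The constant hazard cannot be drawn from Appendices C and D. They say that risk begins with the first overnight period and, for continuous wear, rises with consecutive days between removals. Study lenses are removed each morning, and neither appendix says risk accrues evenly over 3 months.

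Finally, the estimator is inferred, since the safety outcomes section is partly redacted. The inference rests on Sections 8.5.1, 8.5.3, 8.6.1 and 8.6.2; the readable analysis text contains no person-time or time-to-event summary of SAEs.

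**Conclusion.** The point holds at modest size. On the natural reading of the plan, the SAE rate is a crude proportion of dispensed subjects or eyes regardless of wear time, and early discontinuation biases it downward as an estimate of 3-month risk. If the full 28% allowance fell on dispensed subjects, with constant hazard and non-informative exit, the understatement would be about 10% to 26% for exits between Day 60 and Day 7, and at most 28-29%. Losses before dispensing or front-loaded risk reduce it.

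A reader might infer a much larger bias by setting the approximately 90 subjects of the Synopsis and Section 3.1 against the 50 completers of Section 8.3, which implies 40/90 = 44% attrition. The documents do not support that. The only stated allowance is 28% of 70 enrolled, and the difference between 70 and 90 is an unreconciled enrolment figure, not a planned loss. Nor can enrolled be equated with dispensed: lenses are dispensed about two weeks after Screening, and anyone lost in that interval never enters the FAS.

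This is an improvement to consider, not an error that invalidates the safety summary.

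**What to change.** In Section 8.6.2, state the numerator and denominator of the SAE rate, keep the crude percentage, and add two figures beside it:

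1. Subjects with an SAE per 100 subject-months of lens wear, with time counted from first wear to first SAE or last wear.
2. The Kaplan-Meier cumulative incidence of a first SAE at Day 90 from first wear, with a note that it assumes non-informative exit.

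Two conventions should be fixed in advance: how an SAE with onset after last wear but before exit is counted, and whether days of suspended wear during a refit count as exposure (the Section 8.6.7 definition, last minus first date plus 1, includes them).

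Both figures come from the exposure and onset dates already collected. The cost is two extra summary lines and, if any SAE occurs, a slightly less favourable figure.

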8.6.3 Subject Demographics and Baseline Characteristics

Demographics and baseline characteristics will be summarized descriptively for the FAS and PP Set.

8.6.4 Subject Discontinuation

The reasons for study discontinuation will be summarized for the FAS.

8.6.5 Protocol Deviations

Important (major) protocol deviations will be summarized by category for the FAS in a table.

Categories of important protocol deviations leading to exclusion from the PP Set will include the following:

- Ineligibility at screening but treated
- Not dispensed study treatment
- Use of medications that could potentially affect the primary effectiveness endpoint
- Errors in the assessment of the primary effectiveness endpoint
- Compliance with study treatment of less than 80%

Additional important protocol deviation categories may be added prior to database lock.

8.6.6 Treatment Compliance

Lens wear parameters (average number of nights worn per week and average nightly wearing time, in hours) will be summarized using continuous and categorical summary statistics by visit. The overall average number of nights per week, overall average nightly wearing time, and overall compliance (%), estimated for each subject based on visit dates and reported lens wear parameters, will also be summarized. Compliance will be based on an expected wearing time of eight hours per day.

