4.6 Masking/Unmasking

Not applicable; this is an open-label study.

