7. STATISTICAL METHODS

Changes to these statistical plans will be documented in protocol amendments and/or the statistical analysis plan.

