8.5.2 Per Protocol (PP) Set

The PP Set will consist of all FAS subjects without important protocol deviations that could affect the primary effectiveness endpoint. The membership of the PP Set will be determined prior to database lock.

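### Does the 80% compliance cut for the Per Protocol Set need a written formula before it can be used?

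*Combined protocol and SAP*

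**What the plan says.** Section 8.6.6 promises an overall compliance percentage, "estimated for each subject based on visit dates and reported lens wear parameters", and adds that "Compliance will be based on an expected wearing time of eight hours per day". It also promises separate summaries of nights per week and hours per night. Section 6.4 adds only that compliance will be judged from the lens wear data.

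Section 8.6.5 lists "Compliance with study treatment of less than 80" per cent among the deviations that exclude a subject from the PP Set, and notes that "Additional important protocol deviation categories may be added prior to database lock". Section 8.5.2 states that "The membership of the PP Set will be determined prior to database lock". The PP Set has one stated outcome use, in Section 8.6.1: "As a sensitivity analysis, the summary will be produced using the PP Set". The summary in question is the primary effectiveness proportion.

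Eight hours is the required nightly minimum, with wear every night (Section 3.1; Appendix D, Wearing Schedule). Sections 6.1.3 and 6.1.4 tell a subject who is being refitted to stop wearing the study lenses until the new ones arrive, after which the follow-up sequence starts again for that subject.

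**The concern.** A numerical cut is applied to a quantity that has no written formula, and two choices that decide its value are open.

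- **Hours above eight.** Because eight hours is a minimum, longer nights are allowed. If compliance is simply hours worn over hours expected, long nights can offset skipped ones. If average hours are capped at eight, they cannot.
- **Refit nights.** A refitted subject has two sets of early visits, and the text does not say which set starts the count. If the nights without lenses count as expected wear, a subject could be classed as non-compliant for following the protocol.

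The wear items also differ by visit: a count of nights at 1 week, and an average per week from 1 month on. On masking the protocol says "Not applicable; this is an open-label study", so acuity results may be known while the formula is still undecided. At stake is who enters the sensitivity analysis of the primary outcome.

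**Working it through.** The plan prints no compliance figure to reproduce, so the check asks how far the two open choices can move a subject and what moves with them.

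**1. Hours above eight.** Inputs: 8 hours a night and 7 nights a week (Section 3.1; Appendix D), and the 80% cut (Section 8.6.5).

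- Expected weekly wear: 7 × 8 = 56 h. The cut lies at 0.80 × 56 = 44.8 h.
- 5 nights × 9 h: uncapped 45/56 = 80.4% (in); capped 5 × 8/56 = 71.4% (out).
- At exactly 8 h the two versions agree: 44.8/8 = 5.6 nights a week is the boundary.
- At 9 h they disagree only from 44.8/9 = 4.98 to 5.6 nights a week; at 8.5 h, only from 44.8/8.5 = 5.27 to 5.6.

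The disputed band is therefore narrow. A cap does not make the measure strict either: 7 nights × 6.4 h = 44.8 h still scores exactly 80%.

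**2. Refit nights.** Inputs: permitted nights are 1 + 90 = 91 (refit at the 1-Day Visit) or 7 + 90 = 97 (refit at the 1-Week Visit), from the visit targets in Section 3.6. The length of a refit gap is not stated. Section 6.1.2 gives about 15 days for the first order, and applying it here is an assumption.

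| Subject wearing 8 h | Gap left out | 15-day gap counted, 1-Day refit | 15-day gap counted, 1-Week refit |
|---|---|---|---|
| 6 nights in 7 | 6/7 = 85.7% | (6/7) × 91/106 = 73.6% | (6/7) × 97/112 = 74.2% |
| Every night | 100% | 91/106 = 85.8% | 97/112 = 86.6% |

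The 6-in-7 wearer falls below 80% once the counted gap exceeds (6/7) × 91/0.8 − 91 = 6.5 days, or (6/7) × 97/0.8 − 97 = 6.9 days. For assumed gaps of 7 to 25 days the scores run from 79.6% to 67.2% (1-Day refit) and from 79.9% to 68.1% (1-Week refit).

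**3. Which reading the data collection supports.** Section 6.1.9 sends the re-dispensing visit to the Section 6.1.2 assessments, which include no wear items, and Appendix A starts those items at the 1-Day Visit. The repeated 1-Day and 1-Week Visits then report wear of the new lenses. So no scheduled report is designed to cover the gap. Compliance rests on reported wear, and Section 8.6.8 rules out imputation. Leaving the gap out is what an analyst would ordinarily do.

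**4. Effect on the result.** Let s of n PP subjects succeed. Removing a failure raises the proportion by s/(n − 1) − s/n = s/[n(n − 1)], which is at most 1/n. Removing a success lowers it by (n − s)/[n(n − 1)], also at most 1/n. If all completers are in the PP Set, this bound is 1/50 = 2.0 percentage points at the 50 completers of Section 8.3. It is 1/65 = 1.5 points if the 28% loss in that section is applied to the 90 subjects of Section 3.1 (90 × 0.72 = 64.8).

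**The case for a change.** The best argument for a change is that the same wear reports can put a subject in or out of the PP Set, and that fixing membership before lock offers limited protection when investigators and sponsor can see acuity. Section 8.6.7 writes out its exposure formula as a span from first to last wear. Borrowing that span for compliance would count the refit gap. One of the 1-, 2- and 3-Month Visits may also be missed without discontinuation, so a programmer must decide how to treat that interval. A few sentences would settle all of this.

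The facts in that argument stand: there is no equation, and both choices can matter for an individual. Its force is limited. Section 8.6.6 does not point to the exposure span, and exposure is a different quantity. With one arm, no comparator and no hypothesis test (Section 8.2), there is no test for a chosen formula to pass. Nights and hours are tabulated separately, so offsetting would be visible. Section 3.3.3 requires discontinuation of subjects who cannot keep the wearing schedule. It sets no number, so some could remain, but a subject who leaves early would normally have no 3-month acuity and so would not enter the summary.

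**Conclusion.** No change to the plan is needed. This is missing detail that analysts can fill sensibly, not a rule that gives a wrong answer. Section 8.6.6 names the inputs and the expected value. The plain reading is reported hours over expected hours, and a cap would be a preference. The way wear is collected points to leaving refit nights out. The plan also provides a place to record the convention: "Changes to these statistical plans will be documented in protocol amendments and/or the statistical analysis plan". Noting it there when the analysis is programmed, before PP membership is settled, is ordinary good practice.

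The effect is confined to the PP sensitivity proportion, at most 1/n per reclassified subject. The FAS proportion and the serious adverse event rates do not depend on compliance. The individual examples rest on hypothetical wearers and an assumed refit gap. The numbers of refits and of subjects near the cut are not given, so the total shift cannot be estimated from the documents.

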8.6.7 Treatment Exposure

Treatment exposure (days), defined as the difference between the last date of lens wear and the first date of lens wear + 1, will be summarized using continuous summary statistics.

8.6.8 Missing Data

Missing data will not be imputed.

8.6.9 Multiplicity Issues

Multiplicity issues do not pertain to this study because there is no hypothesis testing.

8.6.10 Interim Analyses

No interim analyses are planned.

8. DATA QUALITY ASSURANCE

9.1 Subject Confidentiality

All personal subject data collected and processed for the purposes of this trial will be maintained by the Investigator and his/her staff with adequate precautions as to ensure that the confidentiality of the data is in accordance with local, state, and federal laws and regulations.

Monitors, auditors, and other authorized representatives of CRO, the Sponsor, the IRB approving this trial, the FDA, the Department of Health and Human Services, other domestic government agencies, and other foreign regulatory agencies will be granted direct access to the trial subject's original medical and trial records for verification of the data and/or clinical trial procedures. Access to this information will be permitted to the aforementioned individuals to the extent permitted by law.

A report of the results of this trial may be published or sent to the appropriate health authorities in any country in which the product may ultimately be marketed, but the subject's identity will not be disclosed in these documents.

Suspected data breaches involving Personal Health Information will be escalated to Bausch + Lomb Data Privacy representative per [REDACTED]

